#### **Cerebral MRI (as adopted from )**

Study subjects will be screened for new asymptomatic CVEs, within 24 hours after the ablation procedure and again at 1 month post procedure with 1.5 T MRI. A baseline is not done to minimize the number of imaging studies. The Flair sequencing has the ability to delineate a new embolic lesion from an old infarct. This will help reduce the patient exposure to repeated testing. The imaging protocol includes a sagittal T1-weighted spin echo sequence to obtain a better definition of the anterior and posterior cerebral commissures. The parameters of the T1-weighted spin echo sequence were as follows: repetition time/echo time 400/13; slice thickness 5 mm; distant factor 0%; field of view 230 mm; matrix 192×256; and acquisition time 59 seconds. An axial fluid-attenuated inversion recovery (FLAIR) sequence was then used. The parameters of the FLAIR sequence were as follows: repetition time/echo time 8500/112; TI 2500 ms; slice thickness 5 mm; distant factor 30%; field of view 240 mm; matrix 154×256; and acquisition time 3.24 seconds. A diffusion-weighted (DW) sequence, with the use of a single-shot spin echo with echo-planar imaging technique that combined the motion-probing gradient before and after the 180° pulse with echo-planar imaging readout, was obtained; The parameters of the DW sequence were as follows: repetition time/echo time 3200/99; slice thickness 5 mm; distant factor 30%; field of view 230 mm; matrix 128×128; bandwidth 1502 Hz; gradient strength 22 mT; duration of diffusion gradients 31 ms; gradient separation 42 ms in 3 orthogonal directions; and

acquisition time 43 seconds. For each DW sequence, the apparent diffusion coefficient map will be obtained.

On the post ablation MRI, an acute embolic lesion was defined as a focal hyper intense area detected by diffusion weighted sequence (DWI) with or without addition of delayed Fluid-attenuated inversion recovery (FLAIR) positive sequence. The size and localization of the focal lesions will be analyzed certified by radiologist blinded to the clinical status.

Subjects who have the Cardiac electrical implantable devices who are undergoing MRI examination will follow standard protocol which are in place in the institution.

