### **Neurology Evaluations**

Patients will undergo a NIHSS and EQ5D prior to procedure (within 24 hours) and post (12-48 hours). If changes in the NIHSS score of greater than 3 a neurologist will be consulted, and the patient will be evaluated and treated based on their recommendation. Asymptomatic Cerebrovascular emboli are defined as cerebral infarct present on MRI or CT scan for which no corresponding symptoms were documented [2]. Symptomatic Cerebrovascular emboli were defined as an episode of neurological dysfunction associated with a focal cerebral infarction in the region correlating with the dysfunction. .

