### ***Exclusion Criteria***

#### **A. Target Disease Exceptions**

- History of CVA/TIA in last 3 months
- Cardiac surgery or neurosurgery within 3 months of the intended procedure date

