### Primary End Point Assessment

Incidence of periprocedural embolic events –TIA/CVA/other systemic embolic events immediately after the left ventricular arrhythmia ablation up to 30 days post left ventricular arrhythmia ablation.

The incidence of new asymptomatic cerebrovascular events as documented by MRI at 24-48 hours post procedure and at 30 days after the left ventricular arrhythmia ablation.

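### The acute-lesion rule rests on DWI brightness alone and leaves the ADC map unused, so with no baseline MRI an older silent bright focus can be counted as a new event

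*Combined protocol and SAP*

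**What the plan says.** All the imaging rules are in the Cerebral MRI section.

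- **Lesion rule.** On the post-ablation scan "an acute embolic lesion was defined as a focal hyper intense area detected by diffusion weighted sequence (DWI) with or without addition of delayed" FLAIR positivity. Brightness on DWI suffices; FLAIR neither confirms nor rules out a lesion.
- **ADC.** "For each DW sequence, the apparent diffusion coefficient map will be obtained". No definition, endpoint or analysis refers to the map again.
- **Baseline.** "A baseline is not done to minimize the number of imaging studies". The reason given is that "The Flair sequencing has the ability to delineate a new embolic lesion from an old infarct".

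Other sections bear on whether a lesion is new:

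- **Neurology Evaluations:** "Asymptomatic Cerebrovascular emboli are defined as cerebral infarct present on MRI or CT scan for which no corresponding symptoms were documented". The infarct need not be new.
- **Primary End Point Assessment:** "The incidence of new asymptomatic cerebrovascular events as documented by MRI at 24-48 hours post procedure and at 30 days". Here, and under Primary Objectives, it must be new.
- **Target Disease Exceptions:** the only exclusion by timing of a cerebrovascular event is "History of CVA/TIA in last 3 months".
- **Baseline Visit:** an MRI from the previous 6 months is listed without a body region. The Time and Events Schedule places no cerebral MRI before the procedure.

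**The concern.** The endpoint is meant to count lesions caused around the ablation. Without a pre-procedure scan, the reading rule alone must separate new from old, and it contains nothing that dates a lesion. DWI signal carries T2 weighting (the stated echo time is 99 ms), so an older focus with long T2 can look bright without restricted diffusion. The ADC map is the image that tells these apart. The plan obtains it and then does not use it. The plan's own safeguard, FLAIR, is optional in the rule.

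The population has ischemic or non-ischemic cardiomyopathy, and the 3-month exclusion removes only clinically recognised recent events, so patients with older silent lesions can enter. At stake is the silent-event rate that this pilot is meant to estimate. The Statistical analysis text makes a larger study depend on a positive signal from this one, so an inflated rate could carry over into its planning.

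**Working it through.** **1. Does any text date a silent lesion?** The lesion rule uses brightness only. The asymptomatic definition asks for an infarct without documented symptoms, not a new one. The exclusion works on known events. The 6-month MRI cannot serve as a baseline, because its body region is unstated and the plan says that no baseline is done. Blinding the radiologist to clinical status limits reader bias but does not age a lesion. So the gap is there on the text.

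**2. Can an older focus look bright with these scan settings?** Stated inputs: gradient 22 mT (taken as per metre), duration δ = 31 ms, separation Δ = 42 ms (taken as onset to onset), TE = 99 ms. With γ = 2.675 × 10⁸ rad/s/T,

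b = (γGδ)² × (Δ − δ/3) = (2.675 × 10⁸ × 0.022 × 0.031)² × (0.042 − 0.0103) ≈ 1.054 × 10⁹ s/m², or about 1,054 s/mm².

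Take signal as proportional to exp(−TE/T2) × exp(−b × ADC), ignoring differences in T1 and proton density. Assume normal tissue has T2 = 90 ms and ADC = 0.8 (× 10⁻³ mm²/s). A lesion is brighter than normal tissue only if

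TE/T2 < 99/90 − 1.054 × (ADC − 0.8).

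| Lesion ADC | Right-hand side | T2 needed |
|---|---|---|
| 1.0 | 1.100 − 0.211 = 0.889 | above about 111 ms |
| 1.5 | 1.100 − 0.738 = 0.362 | above about 273 ms |
| 2.0 | 1.100 − 1.265 < 0 | no T2 is long enough |

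So T2 shine-through is possible, mainly where ADC is near normal. The tissue values are assumptions.

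**3. What would it do to the rates?** The plan gives no silent-event rate for left ventricular ablation, so there is no figure of its own to reproduce. Assumed inputs:

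- Control rate 14%: the figure in Overall Risk/Benefit Assessment, which is for AF ablation.
- DOAC rate 7%: no source.
- Share f of patients with an older DWI-bright focus, equal in both arms: 4% to 12%, no source.
- 25 per arm, from Study Management and Sample Size Justification.

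Observed rate = 1 − (1 − p)(1 − f), so observed difference = true difference × (1 − f).

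| f | Control | DOAC | Difference | Risk ratio |
|---|---|---|---|---|
| 0 | 14.0% | 7.0% | 7.0 points | 0.50 |
| 4% | 1 − 0.86 × 0.96 = 17.4% | 1 − 0.93 × 0.96 = 10.7% | 6.7 points | 0.61 |
| 12% | 1 − 0.86 × 0.88 = 24.3% | 1 − 0.93 × 0.88 = 18.2% | 6.2 points | 0.75 |

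Expected false events in the control arm are 25 × 0.86 × f, or 0.86 at 4% and 2.58 at 12%, beside 25 × 0.14 = 3.5 true ones. In the DOAC arm they are 25 × 0.93 × f, or 0.93 and 2.79, beside 25 × 0.07 = 1.75 true ones.

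**4. Does it change what the test can show?** Exact power of the uncorrected two-sided 5% chi-square test at 25 per arm is 0.12 at f = 0, 0.11 at 4% and 0.09 at 12%. For these rates the trial has almost no power with or without the error.

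**The case against.** The strongest reply has four parts.

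- **The reader may already do this.** A certified, blinded radiologist has the map, and the endpoint text asks for new events. But this is a multicenter study, and an unwritten habit that can differ between readers is not a rule. The source that the section was adapted from is not identified in the text, so its full reading criteria cannot be checked.
- **FLAIR.** A reader might infer that making FLAIR positivity mandatory would close the gap. It would not: old gliotic foci can also be FLAIR-bright, and a very early lesion may not yet show. Leaving FLAIR optional is defensible. What remains is that the stated reason for omitting a baseline plays no part in the scoring.
- **Known strokes.** A reader might infer that a patient with a stroke 4 months earlier would be scored as a silent event. The asymptomatic definition covers only infarcts without documented symptoms, and medical history and a pre-procedure NIHSS are collected. A known stroke therefore falls outside it. The exposure is to older silent lesions.
- **Scale.** A risk ratio moving from 0.50 to 0.75 looks severe, but on the same inputs the absolute difference loses less than 1 point. This stands, and so does the point that chance imbalance at 25 per arm affects every baseline factor.

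**Conclusion.** The concern holds in a limited form. As written, the rule can count an older silent DWI-bright focus as a new primary-endpoint event, and the image that would largely prevent this is obtained but unused. The main harm is an inflated silent-event rate in both arms, by 3.4 to 10.3 points in control (17.4 − 14.0 and 24.3 − 14.0) on the assumed inputs. The between-arm difference shrinks mildly, from 7.0 to between 6.7 and 6.2 points. The 14%, the 7% and the 4% to 12% are all assumptions, so the true size is unknown.

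Two stronger readings are not supported. Old infarcts in general would not be scored as new, since brightness at this diffusion weighting needs near-normal ADC or a very long T2. Nor is there ground for saying that the error favours one arm: with randomisation and a blinded reading it should be similar in both, although the text blinds the radiologist to clinical status without naming treatment arm. The point deserves correction because the remedy is cheap, not because it overturns the pilot.

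**What to change.** - **Cerebral MRI, first post-ablation scan:** define an acute lesion as a focal DWI hyperintensity with matching low signal on the ADC map. Do not count DWI-bright foci whose ADC is clearly normal or high.
- **Foci too small to read on ADC:** record them as indeterminate and report the event count both with and without them. Simply dropping them could lose true small emboli.
- **30-day scan:** count as new only lesions absent from the first scan.
- **Neurology Evaluations:** add the requirement that the infarct be new, to agree with Primary Objectives and Primary End Point Assessment.

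**Cost:** a short change to two sections and one more field on the MRI reading form. No extra scan is needed, because the maps are already to be obtained, but the documents do not say how they are read, so some reading time should be allowed for. The drawback is that, with 5 mm slices, some very small true lesions will be classed as indeterminate; their number cannot be estimated from the documents.

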Use of oral anticoagulation after left ventricular arrhythmia ablation is not standard of care at this point and is anecdotally used in high risk patients with LV aneurysms and those with severe LV dysfunction. Even when used post ablation anticoagulation with warfarin is fraught with several practical issues including the time to therapeutic range and the need for bridging with unfractionated or low molecular weight heparin with implications to prolonged length of stay and increased bleeding complications. So, the novel non VKA agents probably are a better fit for this specific situation. Early experience with all four currently available agents (Dabigatran, Rivaroxaban , Apixiban and Edoxaban) for periprocedural anticoagulation seems to be safe and efficacious. DOAC is a direct oral inhibitor of Prothrombin/factor Xa inhibitor and thereby mediates its anticoagulation effect . In the recently published double blind randomized clinical trial DOAC was found to be superior to warfarin in decreasing the risk of stroke and also had fewer complications of bleeding and death in patients with atrial fibrillation/flutter .

We believe that peri-procedural DOAC use for left ventricular arrhythmia ablation will provide effective anticoagulation without increasing bleeding complications and may decrease the incidence of both symptomatic and asymptomatic cerebrovascular events, TIAs and strokes.

Magnetic resonance imaging (MRI) is the most commonly used imaging test to detect acute ischemic stroke and asymptomatic CVEs. There is a natural apprehension about the use of MRI scanning in patient with Cardiac Implantable Electrical Devices (CIEDs) . However, there are protocols in place showing MRI examination of patients with CIEDs with minimal or no side

effects . There is increasing data on the safety of the use of MRI in CIED patients which perhaps led to the participating institutions routine use of MRI in defining ventricular scar prior to RF ablation to optimize the treatment strategy and outcomes. The potential for adverse effects on the CIED during MRI of the head is far lower than imaging the chest as the device will not be in the direct MRI field as it is with head scanning. When performed with appropriate monitoring the post left ventricular arrhythmia ablation MRI scanning of the brain can be safe and help us examine an important issue that has not been well defined.

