## **INVESTIGATIONAL PLAN**

### **Study Design and Duration**

This is a multicenter, randomized, prospective study to determine, if DOAC can be used periprocedural in patients undergoing a scar left ventricular arrhythmia ablation. Patients will be screened from both the clinic setting and upcoming EP lab schedule. The patient's chart will be reviewed and those that meet inclusion/exclusion will be approached for the study. For this study, we intend to enroll 52 consecutive subjects who are undergoing a scar left ventricular arrhythmia ablation at participating institutions if they meet all other inclusion criteria and do not have any exclusion criteria. Patients will be randomized in a 1:1 fashion.

Figure 1 shows the use of ASA or DOAC for left ventricular arrhythmia ablation.

[figure not shown]
Patients undergoing left ventricular arrhythmia ablation will be consented and randomized to either ASA 81 mg or 100 mg daily or DOAC twice daily. Patients randomized to ASA will continue or start ASA 81 mg or 100 mg by mouth daily, and continue up to 30 days after the procedure. Patients randomized to DOAC group will stop the ASA if they are currently taking it; DOAC 5 twice daily will be started 3 hours after hemostasis and continue for 30 days post procedure.

The drugs to which they are assigned to will be continued at least for 30 days post left ventricular arrhythmia ablation. All subjects will be followed from baseline to 30 days post procedure. At this time they will have completed the study and can stop either DOAC and/or Aspirin at the physician's discretion.

*Final revised protocol*

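### The plan's only masking rule for the MRI reading does not name the randomised arm, although MRI lesions are part of the primary endpoint and treatment appears to be open-label

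*Combined protocol and SAP*

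**What the plan says.** **Masking.** The Cerebral MRI section states that the size and localization of lesions "will be analyzed certified by radiologist blinded to the clinical status". Nothing else in the document masks anyone in this trial. The only other mention of blinding, in the Overall Risk/Benefit Assessment, describes a different, cited trial: "In the recently published double blind randomized clinical trial DOAC was found to be superior to warfarin".

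**Treatment.** Study Design and Duration describes the trial as follows: "This is a multicenter, randomized, prospective study to determine, if DOAC can be used periprocedural". It uses neither the term blinded nor open-label. Patients are "randomized to either ASA 81 mg or 100 mg daily or DOAC twice daily". For the control arm: "Patients randomized to ASA will continue or start ASA 81 mg or 100 mg by mouth daily". For the other arm: "Patients randomized to DOAC group will stop the ASA if they are currently taking it". Neither that section nor the Oral Anti-Coagulation/Anti-Platelet Regimen section describes a placebo or dummy.

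**Endpoint.** The primary objective covers stroke and TIA, silent brain lesions on MRI, and systemic thromboembolism. The Primary End Point Assessment lists "The incidence of new asymptomatic cerebrovascular events as documented by MRI", at 24-48 hours and at 30 days. The Cerebral MRI section says that no baseline scan is taken and relies on the imaging sequences to separate new lesions from old.

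**Adjudication.** SAE Reconciliation provides for adjudication of adverse events where there is disagreement. No blinded adjudication of endpoints is described.

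**The concern.** When treatment is visible, masking the outcome assessor is the main remaining protection for an imaging endpoint, and the item to mask is the randomised arm. The rule here names something else and does not define it. If clinical status means symptoms and clinical course, a reader who sees the arm in the chart or on the request form has not broken the rule.

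The rule also covers how large a lesion is and where it lies. The endpoint depends on whether a new lesion is there at all. Calling a small diffusion-weighted focus, and calling it new without a baseline scan, is a judgement. If knowledge of the arm moves that judgement in one arm, the lesion rates differ for a reason unrelated to treatment, and no later analysis can remove the difference. The Statistical analysis text says that a larger study will follow a positive signal, so a reading artefact could influence that decision.

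**Working it through.** The plan gives no figure for reader error, so there is none to reproduce. The check has two parts: how much of the endpoint depends on the reader, and how far an assumed bias would move the comparison.

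**1. Share of the endpoint that depends on the reader**

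Inputs, all from the Overall Risk/Benefit Assessment:
- silent events after AF ablation: 14%
- symptomatic events after AF ablation: 2.3%
- highest quoted stroke rate after left ventricular ablation: 7.5%

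Taking the two kinds of event as separate:
- AF figures: 14 / (14 + 2.3) = 86% silent. Per 25 patients, 0.14 × 25 = 3.5 silent and 0.023 × 25 = 0.6 symptomatic.
- Same 14% with the highest ventricular stroke rate: 14 / (14 + 7.5) = 65% silent.

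The 14% is borrowed from AF ablation. For this population the protocol only projects that silent events may be the more frequent kind, and says that no study has focused on them.

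**2. Effect of an assumed arm-dependent reading**

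Inputs from the plan: 25 analysed per arm (Study Management and Sample Size Justification) and a chi-square test for categorical events (Statistical analysis). The plan does not say whether the test is continuity-corrected and sets no significance level.

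Assumptions made here:
- two-sided 5% level
- true lesion rate of 14% in both arms, so no treatment effect
- a fraction f of lesion-free aspirin patients falsely read as positive, with f = 0, 5% or 10%
- no other reading errors in either arm

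Observed aspirin rate = 0.14 + 0.86 × f:
- f = 5%: 0.14 + 0.043 = 18.3%, an excess of 4.3 points
- f = 10%: 0.14 + 0.086 = 22.6%, an excess of 8.6 points

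The observed DOAC rate stays at 14%. One changed reading moves an arm's rate by 1/25 = 4 points, so these excesses amount to 25 × 0.043 = 1.1 and 25 × 0.086 = 2.2 readings on average.

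For each pair of counts (x_A, x_D) from 0 to 25, the probability is Bin(x_A; 25, p_A) × Bin(x_D; 25, 0.14). These are summed over all pairs with x_A > x_D in which the test is significant. The uncorrected statistic is z = [(x_A − x_D)/25] / √[2 p̄(1 − p̄)/25], with p̄ = (x_A + x_D)/50. The corrected version subtracts 1/25 from the difference. Significance is z > 1.96, or p ≤ 0.05 for Fisher's exact test.

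Chance of a nominally significant DOAC benefit with no true effect:

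| Test | f = 0 (14% vs 14%) | f = 5% (18.3% vs 14%) | f = 10% (22.6% vs 14%) |
|---|---|---|---|
| Chi-square, uncorrected | 2.7% | 6.4% | 12.6% |
| Chi-square, continuity-corrected | 0.6% | 2.0% | 5.0% |
| Fisher's exact | 0.9% | 2.8% | 6.4% |

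The absolute figures depend heavily on the test. The direction does not: under all three, the chance rises several-fold.

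**The case against.** The strongest reply is that clinical status may have been meant to include current treatment. On that reading the radiologist is already masked to arm and only the wording is loose. This stands as far as it goes. A reader might infer from the text that the radiologist will know the arm. The documents do not support that: they are silent on the arm, and silence is not a statement that the reader is unmasked. But an undefined term cannot be audited, and the sentence still omits lesion presence and newness.

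Two other stronger readings are tempting and should not be stated as fact. That the trial is open-label is an inference from visibly different regimens with no placebo; it is a strong inference, but the protocol does not use the term. That MRI lesions will dominate the primary endpoint is a projection based on AF-ablation figures, not on data from this population.

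The size is also open to challenge. No passage gives a reader error rate, so the 5% and 10% are invented for illustration. The uncorrected chi-square gives the largest figures, and with about 3.5 expected lesions per arm a corrected or exact test would be a reasonable choice. All three are therefore shown.

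Finally, the trial is described as a pilot for feasibility and safety, with no formal decision rule. That lowers the stakes. It does not remove them, because the pilot's signal is to decide whether a larger study is done.

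**Conclusion.** The concern holds in this form: masking of the MRI reading to treatment arm is not stated, and the one masking sentence does not extend to the presence or newness of lesions. This matters because MRI lesions are part of the primary endpoint, are projected to be more frequent than symptomatic events, and are judged new without a baseline scan in a trial that appears open-label.

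In the illustration, a false-positive rate of 5% to 10% confined to lesion-free aspirin patients raises the chance of a spurious nominal DOAC benefit to between 2.0% and 12.6%, depending on the test, from a starting point of 0.6% to 2.7%. This shows the possible size of a bias and does not predict that one will occur. It rests on the borrowed 14% rate, equal true rates, a 5% level that the plan does not set, and assumed reader errors. The gap in the wording depends on none of these.

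**What to change.** In the Cerebral MRI section, replace the masking sentence with one stating that the presence, newness, size and localization of lesions on both scans (post-procedure and 30 days) are read by the existing radiologist or radiologists, blinded to treatment arm and to clinical status. Add that the arm is removed from imaging requests and file labels before reading.

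Naming the arm alone would not be enough, because the present sentence would still cover only size and localization. The plan does not say whether reading is central or local. The wording above works for either, but with local reading each site must de-label its own requests.

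The cost is a short change of wording and minor administrative work at sites. It needs no extra reader, scan or patient, and does not change the sample size or clinical management.
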